11.4 Study Record Retention

Study results will be retained in the patient's research record for six years after the study is completed or until the patient reaches the age of 21, whichever is longer. Essential documents should be retained until at least two years after the last approval of a marketing application in an International Conference on Harmonisation (ICH) region and until there are no pending or contemplated marketing applications in an ICH region or at least two years have elapsed since the formal discontinuation of clinical development of the investigational product. These documents should be retained for a longer period, however, if required by the applicable regulatory requirements.

12.0 ADMINISTRATIVE ASPECTS

The following administrative items are meant to guide the Principal Investigator or Sub-Investigator in the conduct of the study but may be subject to change based on industry and government Standard Operating Procedures or Working Practice Documents or Guidelines.

12.1 Confidentiality

All laboratory specimens, evaluation forms, reports, and other records will be identified in a manner designed to maintain research participant confidentiality. All records will be

kept in a secure storage area with limited access. Clinical information will not be released without the written permission of the research participant's guardian except as necessary for monitoring and auditing.

The Principal Investigator or Sub-Investigator and all employees and coworkers involved with this study may not disclose or use for any purpose other than performance of the study, any data, record, or other unpublished, confidential information disclosed to those individuals for the purpose of the study.

12.2 Institutional Review Board Approval

Federal regulations and the ICH guidelines require that approval be obtained from an IRB prior to participation of human research participants in research studies. Prior to the study onset, the protocol, informed consent, any advertisement used to recruit study patients, and any other written information regarding this study to be provided to the research participant or the research participant's legal guardian must be approved by the IRB.

All IRB approvals should be signed by the IRB Chairman or designee and must identify the IRB name and address, the clinical protocol by title and/or protocol number, and the date the approval and/or favorable opinion was granted.

The Principal Investigator or Sub-Investigator is responsible for obtaining continued review of the clinical research at intervals not exceeding one year or otherwise specified by the IRB. The Principal Investigator or Sub-Investigator must supply the Sponsor or its designee with written documentation of continued review of the clinical research.

12.3 Modification of the Protocol

Any changes in this research activity, except those necessary to remove an apparent, immediate hazard to the research participant, must be reviewed and approved by the IRB.

12.4 Informed Consent

A written informed consent in compliance with Part 50 of Title 21 of the Code of Federal Regulations (CFR) and Institutional IRB shall be obtained from each research participant prior to entering the study or performing any unusual or non-routine procedure that involves risk to the research participant.

Before enrollment, each prospective research participant and/or his/her legal guardian will be given a full explanation of the study and be allowed to read the approved informed consent form. Once the Principal Investigator or Sub-Investigator is assured that the research participant/legal guardian understands the implications of participating in the study, the research participant/legal guardian will be asked to give consent to participate in the study by signing the informed consent form.

The Principal Investigator or Sub-Investigator shall provide a signed/dated copy of the signed informed consent to the research participant and/or legal guardian.

12.5 Protocol Violations and Deviations

The Principal Investigator or Sub-Investigator or designee must document and explain in the research participant's source documentation any deviation from the approved protocol. The Principal Investigator or Sub-Investigator may implement a deviation from,

or a change of, the protocol to eliminate an immediate hazard to study research participants without prior IRB approval. As soon as possible after such an occurrence, the implemented deviation or change, the reasons for it, and any proposed protocol amendment(s) should be submitted to the IRB for review and approval, to the Sponsor for agreement, and to the regulatory authorities, if required.

A deviation from the protocol is an unintended and/or unanticipated departure from the procedures and/or processes approved by the Sponsor and the IRB and agreed to by the Principal Investigator or Sub-Investigator. Deviations usually have an impact on individual research participants or a small group of research participants and do not involve inclusion/exclusion or primary endpoint criteria. A protocol violation occurs when there is nonadherence to the protocol that results in a significant, additional risk to the research participant, when the research participant or Principal Investigator or Sub-Investigator has failed to adhere to significant protocol requirements (inclusion/exclusion criteria) and the research participant was enrolled without prior Sponsor approval, or when there is nonadherence to FDA regulations and/or ICH GCP guidelines.

The IRB should be notified of all protocol violations and deviations in a timely manner as required by the site's IRB.

12.6 Study Reporting Requirements

By participating in the study, the Principal Investigator or Sub-Investigator agrees to submit reports of serious adverse events according to the timeline and method outlined in the protocol. In addition, the Principal Investigator or Sub-Investigator agrees to submit annual reports to his/her IRB as appropriate. The Principal Investigator or Sub-Investigator or S

12.7 Study Conduct

The Principal Investigator agrees that the study will be conducted according to the principles of the ICH E6 Guideline on GCP and the principles of the World Medical Association Declaration of Helsinki. The Principal Investigator will conduct all aspects of this study in accordance with all national, state, and local laws or regulations.

12.8 Publications

Following completion of the study, the data may be considered for reporting at a scientific meeting or for publication in a scientific journal. In these cases, Duke University will be responsible to determine how the manuscript is written and edited, the number and order of authors, the publication to which it will be submitted, and other related issues.

14.0 APPENDICIES

Appendix 1: Safety Questionnaire

SAFETY QUESTIONNAIRE

Patient Name:									
Date completed:			/		/				
-	m	m	d	d	у	у	у	у	

Please answer the following items regarding your child to the best of your ability. Some of the questions may be the same as the questions you answered previously.

Since your child's last study visit, did any of the following occur?

- 1. Was your child hospitalized?
 - θ Yes; if so, why?
 - θ Νο
- 2. Did your child develop a tumor?
 - θ Yes
 - θ Νο
- 3. Did your child develop abnormal skin lesions?
 - θ Yes
 - θ Νο
- 4. Was your child diagnosed with cancer?
 - θ Yes
 - θ Νο
- 5. Did your child have a serious infection?
 - θ Yes
 - θ Νο
- 6. Was your child diagnosed with an autoimmune disease?
 - θ Yes
 - θ Νο
- 7. Did your child require a blood transfusion?
 - θ Yes
 - θ No
- 8. Has your child developed any other health problems not described above?
 - θ Yes; if so, what?
 - θ No
- 9. Has your child developed any new onset seizures?
 - θ Yes
 - θ Νο
- 10. Has your child started any new medications?

- θ Yes; if so, which ones?
- θ Νο
- 11. Has your child's diet changed (i.e. started/stopped a special type of diet)?
 - θ Yes; if so, how?
 - θ Νο
- 12. Have you noticed an increase in any of the following in your child since their last visit? Select all that apply.

	Appetite (increased or decreased)	θYes	θΝο
	Fatigue	θ Yes	θΝο
	Headache	θ Yes	θΝο
	Restlessness	θ Yes	θΝο
	Tremor	θ Yes	θΝο
13. Has y	our child participated in any of the following:		
	Other cell therapy	θ Yes	θΝο
	Immune therapy (i.e. IVIG, steroids)	θ Yes	θΝο
	Other clinical trials	θYes	θΝο
	If yes, please describe:		

Please describe any changes you have seen in your child since receiving their first infusion:

Please rate your child's development in the following domains since receiving their first infusion (Circle the number that corresponds best.):

1	2	3	4	5				
Slowed	Stayed	Improved	Improved	Improved				
down	about the	a little	more than	much				
	same	more than	expected	more than				
		expected		expected				
1. Fine Motor (u	se of hands/fingers f	or activities like hold	ling toys, playing, dı	rawing, eating, etc)				
1	2	3	4	5				
2. Gross Motor (running or climbin	(use of big muscles for ng)	or activities like head	l control, rolling, cra	wling, walking,				
1	2	3	4	5				
A	-	~	•					
3. Receptive Lan	iguage (language list	ening and understan	ding, following spok	ten requests, etc.)				
1	2	3	4	5				
				_				
4. Expressive La	nguage (speaking sk	ills: use of signs, wo	ords, sentences, etc.)					
1	2	3	4	5				
-			-					
5. Cognitive Skil	ls (thinking, learning	, reasoning, and pro	blem solving)					
1	2	3	4	5				
				_				
6. Adaptive and Self Help Skills (feeding, dressing, toileting, etc.)								
1	2	3	4	5				
1	-		•					
7. Social Skills and Behavior (interpersonal skills, peer skills, emotions, behaviors)								
1	r	2	А	E				
1	L	3	4	3

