The median baseline age of participants was 3.7 years (range 1.4-6). Sibling CB infusions had a median TNCC of 4.3×10^7 /kg (range 1.8-5.2) and median CD34 dose of 0.6×10^5 /kg (range 0.1–1.8). Four CB infusions were full HLA matches, 11 were haploidentical. All CB units had negative post-thaw sterility cultures. There were no acute infusion reactions and no unexpected imaging findings. No platelet antibodies, donor-specific HLA antibodies, or donor cells were detected in peripheral blood six months after infusion. With a median follow-up of 11 months, there were a total of 34 adverse events in 13 participants. Most (19/34) were attributed to common childhood infections, and none were related to the CB infusion. The only serious adverse event was unrelated to the infusion and occurred in a participant with a history of seizures who was hospitalized for a prolonged febrile seizure 5 months after CB infusion. Six months after infusion, participants improved a mean of 4.8 (SD 2.5) points on the GMFM-66 and 1 (SD 2.9) point on the Peabody Gross Motor Quotient. This study confirms that partially or fully-HLA matched **allogenenic** sibling CB infusion is safe and feasible in young children with CP.

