5.3 Exclusion Criteria

- 1. Available qualified autologous cord blood unit.
- 2. Hypotonic or ataxic cerebral palsy without spasticity.
- 3. Autism and autistic spectrum disorders.
- 4. Hypsarrhythmia.
- 5. Legally blind.
- 6. Intractable seizures causing epileptic encephalopathy.
- 7. Evidence of a progressive neurologic disease.
- 8. Has an active, uncontrolled systemic infection or documentation of HIV+ status.
- 9. Known genetic disease or phenotypic evidence of a genetic disease on physical exam.
- 10. Concurrent genetic or acquired disease or comorbidity(ies) that could require a future allogeneic stem cell transplant.

- 11. Requires ventilatory support, including home ventilator, CPAP, BiPAP, or supplemental oxygen.
- 12. Impaired renal or liver function as determined by serum creatinine >1.5mg/dL and/or total bilirubin >1.3mg/dL except in patients with known Gilbert's disease.
- 13. Possible immunosuppression, defined as WBC <3,000 cells/mL or absolute lymphocyte count (ALC) <1500 with abnormal T-cell subsets.
- 14. Patient's medical condition does not permit safe travel.
- 15. Previously received any form of cellular therapy.

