6.6 Safety Follow-up

On Day 1 following the infusion, the participant will be seen by study staff to assess for any infusion related adverse reactions or complications. At ~2 weeks post-infusion, a member of the study team will contact the parent or guardian via phone or email to assess patient status and any adverse events. In-person safety assessments will occur at each study visit. In addition, a questionnaire (see Appendix 1) will be administered at 6, 12, and 24 months post baseline visit to assess for serious adverse events.

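### The safety questionnaire's only seizure item is limited to new-onset seizures, so worsening of known seizures is not prompted for, mainly in the remote follow-up of months 12 to 24

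*Combined protocol and SAP*

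**What the plan says.** Section 6.6 describes the questionnaire's schedule and purpose: "a questionnaire (see Appendix 1) will be administered at 6, 12, and 24 months post baseline visit to assess for serious adverse events". Item 9 is the only item in Appendix 1 that names seizures. It reads "Has your child developed any new onset seizures" and offers Yes or No with no space for detail.

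The seizure-related exclusions in section 5.3 are hypsarrhythmia and "Intractable seizures causing epileptic encephalopathy". A child with controlled seizures, or with seizures that fall short of that description, is not excluded on this ground.

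Four other parts of the form could receive a report of worse seizures:

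- item 1, "Was your child hospitalized", which asks for the reason;
- item 8, "Has your child developed any other health problems not described above", with free text;
- item 10, "Has your child started any new medications", with free text;
- the open prompt, "Please describe any changes you have seen in your child since receiving their first infusion".

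Outside the form, section 6.6 provides a day-after assessment, a contact at about two weeks and in-person safety assessments at study visits. Section 7.9 schedules a history and physical at baseline, 6 and 12 months in every arm, and also at 3 months in the MSC arm. Section 9.2 requires every adverse event reported or observed from enrolment onward to be recorded. The secondary endpoint in section 4.3 is the number of adverse events over the 12 months after infusion.

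**The concern.** A parent whose child already has seizures, and whose seizures become more frequent, longer or more severe, can correctly answer No to item 9. The one question aimed at this kind of event therefore does not prompt for it in the children most likely to have seizures.

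The plan's own background makes such children and such events foreseeable. Section 2.6.5 reports that the sibling cord blood trial also excluded intractable seizures, yet its only serious adverse event "occurred in a participant with a history of seizures who was hospitalized for a prolonged febrile seizure 5 months after CB infusion". Item 12 of the same form already asks about increases in milder symptoms such as headache and tremor, so asking about change in an existing problem is within the form's scope.

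What is at stake is the completeness of adverse-event capture, which feeds the secondary endpoint.

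**Working it through.** The plan states no figure on this point, so the check is mainly textual.

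**Step 1: can affected children enrol?** Section 5.3 removes two seizure presentations and no others. The sibling trial, with a comparable exclusion, enrolled a child with a seizure history. So yes.

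**Step 2: what does the form record when known seizures worsen?**

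| Course in a child with known seizures | Item 9 | Other route on the form |
|---|---|---|
| Admitted to hospital | No | Item 1, with the reason |
| Not admitted, new drug started | No | Item 10, with the drug named |
| Not admitted, no new drug (for example, dose of an existing drug changed) | No | Only if volunteered under item 8 or the open prompt |

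Item 8 asks about problems that have developed, so a parent may not think of a worsened existing condition. The open prompt would accept such a report but does not ask for it. The third row is the gap.

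**Step 3: when does the gap matter?** Through month 12, each arm has in-person visits with a history and physical. After month 12, sections 7.9 and 8.3 leave a single remote assessment at 24 months. The form's items look back to the last study visit, so recall at that point spans about 12 months.

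- AlloCB and MSC arms: counted from first infusion, the 12-month window is months 0 to 12, which the visits cover.
- Natural history arm: infusion is at 12 months (section 4.1), so the window is months 12 to 24. The day-after and two-week contacts cover its start. About 52 − 2 = 50 of 52 weeks then rest on the remote assessment.

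**Step 4: how many children does the wording concern?** The documents give no share with a seizure history. Assuming 20% to 40%:

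- all arms: 0.20 × 90 = 18 to 0.40 × 90 = 36;
- natural history arm: 0.20 × 30 = 6 to 0.40 × 30 = 12.

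These count children with a seizure history. Turning them into missed events would need a worsening rate and a capture rate, and the documents give neither.

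**Step 5: context from section 8.5.** The table there gives the probability of seeing at least one event among 30 children, 1 − (1 − p)^30. It reproduces: 26.0% at p = 1%, 78.5% at 5% and 95.8% at 10%. The calculation takes every event as captured. If only a fraction c is captured, the formula becomes 1 − (1 − cp)^30. The values of c below are assumptions.

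| True rate p | c = 100% | c = 75% | c = 50% | c = 25% |
|---|---|---|---|---|
| 10% | 95.8% | 90.4% | 78.5% | 53.2% |
| 5% | 78.5% | 68.2% | 53.2% | 31.4% |

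This shows why capture matters in general. It does not estimate the loss here, because the gap affects one kind of event in a subset of children.

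**The case against.** The strongest reply is that No to item 9 is not No on the form. A reader might infer that worsening seizures go unrecorded, or that the sibling-trial event would be missed here. The documents do not support either inference. That event was a hospitalisation, so item 1 would record it with its reason. Section 2.6.5 also states that it was unrelated to the infusion, so it is not evidence of harm from the product. It shows only that children with prior seizures enter such trials and have seizure events.

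A reader might also infer that a low seizure count would be falsely reassuring. Nothing in the plan tabulates or interprets item 9 alone. Section 8.6.4 summarises adverse events from all sources, and section 9.4 draws on any data collected in the study.

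Two further replies have weight. Section 6.6 gives the form's purpose as finding serious events, and worsening without admission will often not be serious. And the in-person visits do cover year one.

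These replies shrink the point without removing it. Section 9.2 and the secondary endpoint cover all adverse events, and the form itself asks about non-serious matters such as fatigue and diet. After month 12 no in-person history backs it up, apart from the natural history arm's day-after assessment. The month 12 to 24 contact is also not quite the only one: that arm has its two-week contact as well.

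**Conclusion.** The point holds in a narrow form. The only seizure item does not prompt for worsening of known seizures, although children with non-intractable seizures are eligible. What may be missed is worsening with no admission and no new drug, mainly between months 12 and 24. This bears most on the natural history arm, where that period is nearly all of the post-infusion adverse-event window.

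The number of events at risk cannot be derived from the documents. The 18 to 36 children rest on an assumed 20% to 40% share. The timing argument takes the last assessment to be 24 months after baseline, as in sections 6.6 and 8.3.

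This is a cheap improvement to data collection. It does not touch the primary endpoint or the sample size.

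**What to change.** Reword item 9 to ask whether the child has had any new seizures, or whether existing seizures have become more frequent, longer or more severe, and add a date and a free-text description. Record seizure history as a baseline field, taken from the history and physical already scheduled, so that later reports can be interpreted against it.

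The cost is one reworded item and one baseline field, with no added visit. The downside is that some ordinary fluctuation in known epilepsy will be reported and will need review.
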